4 STUDY METHODS

4.1 Overall Study Design and Plan

This is a multi-center, double blind, placebo-controlled study that will investigate the efficacy and safety of pomalidomide in patients with HHT and chronic epistaxis with iron-deficiency anemia and/or requiring intravenous iron infusions or blood transfusion.

After recruitment, patients will be screened for study eligibility. The screening evaluation will include the ESS with three-month recall, which will reflect the patient's history of epistaxis and bleeding over the prior three months, as well as detailed review of iron infusion and red cell transfusion over the preceding six months. Eligible patients will be provided a diary to record the duration of each epistaxis event that occurs during the 4-week period between screening and baseline visits. Eligible patients will then return for the randomization visit between 28 and 56 days later, at which time patients will undergo genetic testing if this has not been previously performed or if results for ENG, ACVRL1 and SMAD4 genes are not available. A repeat ESS with 4-week recall will be performed and will be considered the "baseline" ESS. Patients will also take QOL surveys at this visit. Patients will then be randomized 2:1, stratified by study site, to either pomalidomide, 4 mg/day for 28 days during each of six 28-day cycles (24 weeks), or placebo, administered on an identical schedule.

Patients will be seen every four weeks during the study (visits C1-C6 at weeks 4, 8, 12, 16, 20, 24 and 4-weeks post treatment follow-up) to measure the ESS (with 4-week recall, see **Appendix 1**), measure iron stores, and obtain laboratory studies, which will include CBC, metabolic profile, and iron studies. The iron replete state will be defined as a ferritin ≥ 50 ng/ml and a transferrin saturation $\geq 30\%$ (since ferritin levels may be elevated due to concurrent inflammation). Investigators will be encouraged to replete iron stores in patients in both arms of the study based on these parameters, and the amount of iron infused (in mg) recorded. There is no mandate for the use of a particular iron preparation. Investigators will be encouraged to use iron infusions prior to blood transfusion, though the latter will be mandated for a hemoglobin below 6.5 gm/dl and recorded as units of packed red blood cells administered. Blood transfusion may also be given at the investigator's discretion based on symptoms that may include shortness of breath, severe fatigue, or other cardiovascular manifestations. Patients will be assessed for adverse events (AE) throughout the study. Treatment dosage may be reduced, or temporarily or permanently discontinued following AE-specific guidelines related to fatigue, cytopenia, or other toxicities.

The 4-week diary of epistaxis events (see **Appendix 2**) will be recorded at selected intervals between visits throughout the study (weeks 8-12 and 20-24 as well as 0-4 weeks post treatment follow-up). The diary was collected from participants via a phone app developed by RTI available for all smart phones, or as a paper diary for participants without access to a smartphone.

The effect of pomalidomide on QOL will be assessed at the baseline visit, at the 12- and 24-week visits, and at the 4-week post-treatment follow-up visit using validated NIH instruments of 1) NeuroQoL satisfaction with social roles and activities, 2) PROMIS emotional distress – depression, and 3) PROMIS fatigue. We will also assess responses to an HHT specific questionnaire developed specifically for this study and shown to correlate with these PROMIS items. The effect of pomalidomide on duration of epistaxis will be assessed at the 12 and 24-week treatment visits and at the 4-week post-treatment follow up visit.

4.2 Study Population

The study population is defined by the following eligibility criteria.

Inclusion Criteria:

1. A clinical diagnosis of HHT as defined by the Curacao criteria
2. Age > 18 years
3. Platelet count $\geq 100 \times 10^9/L$
4. WBC $\geq 2.5 \times 10^9/L$
5. INR ≤ 1.4 and normal ± 2 sec activated partial thromboplastin time (aPTT or PTT per local laboratory designation) by local laboratory criteria (except for patients on a stable dose of warfarin or direct oral anticoagulants)
6. Epistaxis severity score ≥ 3 measured over the preceding three months, measured at the screening visit
7. A requirement for anemia, as determined by local laboratory hemoglobin assessment and normal ranges, and/or parenteral infusion of at least 250 mg of iron or transfusion of 1 unit of blood over the 24 weeks preceding the screening visit
8. All study participants must agree to be registered into the FDA mandated POMALYST REMS® program, and be willing and able to comply with the requirements of the POMALYST REMS® program
9. Females of childbearing potential (FCBP) must adhere to the pregnancy testing schedule mandated by the POMALYST REMS® program.
10. Ability to understand and sign informed consent

Exclusion Criteria:

1. Women currently breast feeding or pregnant
2. Renal insufficiency, serum creatinine > 2.0 mg/dl
3. Hepatic insufficiency, bilirubin > 2.0 (or > 4.0 in the setting of a prior clinical or genetic diagnosis of Gilbert's syndrome) or transaminases $> 3.0 \times$ normal
4. Prior treatment with thalidomide or other Immunomodulatory imide drugs (IMiDs) within previous 6 months
5. Prior treatment with bevacizumab (systemic or nasal) within previous 6 weeks
6. Prior treatment with pazopanib within previous 6 weeks
7. The use of octreotide or oral estrogens within the previous month
8. History of prior unprovoked thromboembolism confirmed by venous ultrasound or other imaging modalities
9. Known peripheral neuropathy, confirmed by neurologic consultation
10. Known underlying hypoproliferative anemia (i.e., myelodysplasia, aplastic anemia)
11. Currently enrolled in other interventional trials
12. Known hypersensitivity to thalidomide or lenalidomide.
13. The development of erythema nodosum if characterized by a desquamating rash while taking thalidomide or similar drugs.
14. Known SMAD-4 mutation
15. Anything that in the investigator's opinion is likely to interfere with completion of the study

4.3 Study Arm Assignment and Randomization

159 randomized individuals are required for this study. Randomization will be performed at a 2:1 (pomalidomide:placebo) manner to enhance patient enthusiasm for participation in the trial.

Randomization is completed within the Medidata EDC system. Randomization is stratified by site using a permuted block design with randomly varying block sizes of 3 and 6. For further details on randomization see the **PATH-HHT Randomization Specification**.

4.4 Masking and Data Lock

4.4.1 General Masking Procedures

This is a double-blind, placebo-controlled clinical trial. As such, neither the participant receiving study drug nor the site staff that administers study procedures and assessments will be aware of the treatment assignment. Additionally, all members of the clinical coordinating center at Cleveland Clinic including PI [name] and the data coordinating center at RTI including DCC PI [name] are masked except for statisticians responsible for developing the randomization schedule, coordinating study drug supplies with Celgene, and producing DSMB reports. Any intentional or unintentional unmasking will be reported as a protocol deviation in the data management system. For further details on masking and procedures for unmasking see the **PATH-HHT Blinding Plan**.

4.4.2 Database Lock

The database will be locked at the completion of study follow-up. Randomization assignment will not be unmasked beyond the details in the blinding plan until after database lock is finalized.

4.5 Study Flow Chart of Assessments and Evaluations

Visit	Screen and Baseline		Treatment Period						End of Study	
	SC	BL	C1	C2	C3	C4	C5	C6	EOS	ET
Study Procedures	Week -4 to -8	Week 0	Week 4 0-5 Days	Week 8 0-5 Days	Week 12 0-5 Days	Week 16 0-5 Days	Week 20 0-5 Days	Week 24 0-5 Days	Week 28 (4 week follow up) 0-7 Days	Only for withdrawn consent
Informed Consent	X									
Enrollment Criteria	X									
Demographics	X									
Medical History	X									
Concomitant Medications	X	X	X	X	X	X	X	X	X	X
Physical Exam	X	X ^{1*}	X ¹	X ¹	X	X ¹	X ¹	X	X	X
Vital Signs ²	X	X	X	X	X	X	X	X	X	X
Genetic Testing ³		X								
Iron Infusion	X ⁴	X	X	X	X	X	X	X	X	X
Blood Transfusion	X ⁴	X	X	X	X	X	X	X	X	X
Adverse Events		X	X	X	X	X	X	X	X	X
ESS	X ⁵	X	X	X	X	X	X	X	X ⁵	X
Epistaxis Duration Diary	X	X ⁶		X	X ⁶		X	X ⁶	X ⁶	
CBC with differential	X	X	X	X	X	X	X	X	X	X
CMP	X	X	X	X	X	X	X	X		X
Iron Studies ⁷	X	X	X	X	X	X	X	X	X	X

Visit	Screen and Baseline		Treatment Period						End of Study	
	SC	BL	C1	C2	C3	C4	C5	C6	EOS	ET
Study Procedures	Week -4 to -8	Week 0	Week 4 0-5 Days	Week 8 0-5 Days	Week 12 0-5 Days	Week 16 0-5 Days	Week 20 0-5 Days	Week 24 0-5 Days	Week 28 (4 week follow up) 0-7 Days	Only for withdrawn consent
INR and aPTT	X									
Biorepository Collection	X ⁸	X ^{8*}			X ⁸			X	X ⁸	X
QOL ⁹ surveys		X			X			X	X	X
Pregnancy Testing ¹⁰	X	X	X	X	X	X	X	X		
Randomization		X								
Drug Dispensation		X	X	X	X	X	X			
Drug Return			X ¹¹	X ¹¹	X	X ¹¹	X ¹¹	X		X

SC = Screening; BL = Baseline; C = End of cycle; ESS = Epistaxis severity score; CBC = Complete blood count; CMP = Complete metabolic panel; EOS = End of study Visit; ET = Early termination; QOL = Quality of life; Gray shaded boxes denote flexibility to perform visits remotely in which case physical exam may be modified; vital signs and biorepository samples may not be collected.

¹ Limited physical examination; *A detailed physical exam if screening visit was remote.

² Vital signs will include body weight, blood pressure, pulse and O₂ saturation.

³ Genetic testing will be performed only if not done previously and consent is obtained.

⁴ Information on Iron infusion and Blood transfusion over the past 6 months to be collected at screening visit.

⁵ ESS will be a 3-month recall for these visits; for all other visits, it will be a 4-week recall.

⁶ Epistaxis Duration Diary will be collected at these visits and if applicable a new diary will be dispensed for the next recording.

⁷ Iron studies include ferritin levels, serum iron and total iron binding capacity.

⁸ One PAXgene RNA tube is included at these visits; ^{8*} One PAXgene RNA tube will be included if screening was remote.

⁹ QOL questionnaires will include 3 NIH instruments (NeuroQoL Satisfaction with Social Roles and Activities Short Form V1.1, PROMIS Depression Short Form V1.0 and PROMIS Fatigue Short Form V1.0) and an HHT specific questionnaire.

¹⁰ In FCBP, pregnancy tests will be performed 10-14 days before, and within 24 hours of study drug order. During the first treatment cycle, weekly pregnancy testing is mandated. Thereafter, pregnancy testing will be performed once every 4 weeks, during each cycle of treatment, preferably during the middle of the treatment cycle.

¹¹ Information on remnant drug and empty bottles will be collected over phone, email, or other means, if visit is remote.

5 ANALYSIS POPULATIONS

Randomization can occur either shortly before or at the baseline visit.

- If the screening visit was completed in-person, randomization can be completed before the baseline visit and study drug is ordered by the site from McKesson (manager of the study drug for Celgene and implementer of the Pomalidomide REMS system) to be shipped to the site so it is available at the site on the day of the baseline visit.
- If the screening visit was completed remotely, then eligibility is confirmed at the baseline visit and randomization occurs at baseline, and the drug is ordered to ship directly to the participant or to the site for dispensing to the participants within a few days of the baseline visit.

Under these scenarios, occasionally a randomized participant might withdraw consent before receiving the study medication from McKesson. Participants might also withdraw consent after receiving study medication but before the first follow-up visit and they may refuse to provide any follow-up assessments. Because these patients have no efficacy data to contribute to the analysis, they are excluded from the efficacy analysis populations, as follows:

Modified Intention-to-Treat Population (mITT)

The modified intention-to-treat population will comprise of all randomized participants who took at least one dose of the double-blind study medication AND have at least one post-baseline efficacy measurement.

Note that if a participant receives study drug sent by McKesson and does not return a full drug bottle to the site, it is assumed that they took at least some study drug.

Participants who receive study drug but do not complete the study will be used in all analyses for which data are available. Participants who withdraw consent for further follow-up will be treated as lost to follow-up at the time that consent was withdrawn, and data will be used up to the time of study withdrawal.

Per-Protocol Population (PP)

The per-protocol population will comprise of all randomized participants who complete the study with no major protocol violations and took at least 80% of the prescribed double-blind medication. Participants who were lost to-follow-up will be considered non-compliant for the purposes of the per-protocol population.

The blinded data review meeting identified the per-protocol exclusions as the following:

- Participants who did not take at least 34 pills of study drug (20%) for reasons other than AEs/side effects,
- Participants discontinued due to lost to follow-up or withdrawal of consent,
- One case of discontinuation due to joint decision of PI and participant, and one case due to PI decision,
- Two participants who discontinued study drug due to AEs but continued in the study with efficacy assessments for multiple months after study drug discontinuation.

Safety Population (SAF)

The safety population will comprise all participants that receive any study drug, irrespective of amount or duration of treatment.

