**Discontinuation Rate:** Table 6 also summarizes early study discontinuation rates for HHT study participants, either due to drop-out (from placebo or treatments with minimal side effects), or due to AEs (from our pilot study of pomalidomide and studies of the more toxic thalidomide). Based on an average of these sources, we anticipate a 10% discontinuation rate during the 24-week treatment interval. Patients with HHT regularly see their doctors and are not expected to be lost to follow-up, and so we anticipate being able to obtain post-baseline ESS scores even for participants who stopped taking the double-blind study drug before that time. We also expect to minimize study discontinuations by allowing patients with some side effects to temporarily halt study drug and then re-start with a lower dose. Nevertheless, it is likely that some participants may discontinue the study without providing any post-baseline data, and it is possible that discontinuations due to AE may be larger than 10%. By planning for 90% power with a 10% discontinuation rate, we plan to have sufficient sample size so that the study would still be well powered if the study discontinuation rate were as high as 30%.

Author	Treatment	N	ESS Baseline mean (SD)	Post-trt assessment time	Rate of Discontinuation, dose-limiting AEs or missing data	ESS Post-BL mean (SD)	ESS Change from baseline Mean (SD), N	Source of SD for change from baseline
[name] pilot study of Epistaxis and GI bleeding	Pomalidomide	9 (8 with epistaxis, 1 with GI bleeding)	5.9 (1.47) N=7 (1 recent enrollment not yet included)	12W	22% (2/9) due to rash at 2W.	3.5 (0.99) N=5	-2.5 (2.11), N=5	Calculated from data
				24W		3.3 (0.61) N=5	-2.7 (1.92), N=5	
Whitehead NOSE study (JAMA 2016) Randomized, double-blind	Bevacizumab, estriol, tranexamic acid, or placebo nasal spray (There were no differences between the 4 TRT groups)	121	5.4 (1.38) N=120	12W	12% (6% patient decision, 6% missing diary data or protocol violation)	3.7 (1.68) N=105	-1.5 (1.48), N=105 By trt grp: B: -1.6 (1.2) E: -1.4 (1.5) TA: -1.4 (1.6) Placebo: -1.7 (1.6)	Calculated from data provided by Author
				12W after TRT stop		4.1 (1.65) N=83	-1.0 (1.53), N=83 SD varied by trt grp: (1.3, 1.3, 1.7, 1.8)	
Dupuis-Girod ELLIPSE study (JAMA 2016) Randomized double-blind	Bevacizumab or placebo nasal spray	80	N/A	6 months	8 % (6% patient decision, 2% missing data or protocol violation)	N/A	N/A	N/A

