Calculation Method	Std Dev	Planned study early D/C rate	Power
T-test	1.7	10%	90%
MMRM*	1.7	10%	94%
T-test	1.7	20%	87%
MMRM*	1.7	20%	92%
T-test	1.7	30%	81%
MMRM*	1.7	30%	90%
T-test	1.8	10%	87%
MMRM*	1.8	10%	91%
T-test	1.8	20%	83%
MMRM*	1.8	20%	89%
T-test	1.8	30%	76%
MMRM*	1.8	30%	87%

Note: MMRM includes adjustment for baseline assuming a correlation of -0.4 between baseline and change from baseline, and assumes 10% have no post-baseline data, and half of the remaining drop-outs occur between the first and second post-baseline visits.

**Table 8.** Power Sensitivity Analysis for N=159, Mean Difference=-1.0 and Alpha = 0.044.

With 159 patients, we will also have at least 90% power to identify a treatment group difference of 30% for a binary secondary endpoint of proportion of participants requiring at least one packed red blood cell transfusion or iron infusion at any time during the 24-week treatment period with  $p < 0.05$ , whether assuming a rate in the placebo and pomalidomide groups of 90% and 60%, or 50% and 20%, as demonstrated in Table 9.

Total sample size.	Planned discontinuation rate	Planned sample size (completers)	Power for selected proportions (Pomalidomide vs placebo)	
			60% vs 90%	20% vs 50%
159 (106:53)	10%	144 (96:48)	98%	96%
159 (106:53)	20%	126 (84:42)	97%	93%
159 (106:53)	30%	111 (74:37)	94%	90%

**Table 9.** Power for comparison of treatment groups for proportion of patients with at least one packed red blood cell transfusion or iron infusion during the treatment period for 2:1 randomization with Alpha = 0.05.

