9 EFFICACY ANALYSES

9.1 Overview of Efficacy Analysis Methods

- All efficacy analyses will be performed on the mITT population, the primary population.
- All efficacy variables will be summarized by treatment group at baseline and at subsequent study time points at which assessments were administered and collected. Count (N), mean, standard deviation, minimum, and maximum will summarize continuous efficacy variables, whereas number and percent will summarize categorical efficacy variables.
- Unless otherwise noted, all analyses of dichotomous outcomes, measured at respective time points, will be performed using models as specified in Section 9.3. Efficacy models will be adjusted for stratification by clinical site. Baseline value will be an additional covariate for all analyses of change from baseline scores. Consistent with the description of the primary analysis in the protocol, analyses of primary and secondary outcomes will also include an independent variable for study visit. For analysis of measures assessed at multiple time points (for example, C1 and C6), longitudinal modeling will be used and the interaction between time and treatment groups will be included. Unless otherwise noted, all analyses of continuous efficacy variables (e.g., ESS and QOL scales) will be performed using general linear mixed models. Variables with distributions substantially different from normal will be transformed prior to analysis.

Models will be adjusted for pooled clinical site. If there are not enough patients per clinical site, similar sites will be combined (see Section 7.6)

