9.3.1 Sensitivity Analyses

Per-protocol population

The primary analysis will be repeated on the per-protocol population.

Imbalanced covariates

If there are important baseline characteristics that substantially differ between randomized treatment groups by chance, additional sensitivity analyses may be conducted to evaluate the impact of adjusting for those imbalances.

Clinical Site Effects

We will examine descriptively whether the treatment effect varies across sites.

Removing 12-week post-treatment data

A supportive analysis of the 4-week post-treatment assessment time will be completed for the MITT population with removal of the 20 patient visits that were conducted at 12 weeks post-treatment.

Missing data

The MMRM analysis approach assumes missing data due to missed visits or early study discontinuations are missing at random (MAR). If a statistically significant difference between treatment groups is observed in the primary analysis, then a sensitivity analysis will be conducted on the primary outcome to assess the robustness of the primary analysis to the MAR assumption using methods that assume that data are missing not at random (MNAR). Specifically, we will use multiple imputation of missing data to generate multiple imputed complete datasets (no missing data through 24 weeks), conduct analysis of covariance for change from baseline at 24 weeks on each dataset (model change from baseline at 24 weeks = baseline value + site + treatment group), and use Rubin's rule to combine results across the imputed datasets to obtain a comparison of treatment groups (Ratitch, 2014). We will explore 2 sensitivity analyses: (a) impute missing outcomes in the

pomalidomide treatment group (and the placebo group) based on data from the placebo group (control-based imputation), and (b) impute missing outcomes in the pomalidomide group at varying percentages of the observed values (while imputing missing placebo data based on observed placebo values) until a statistically significant treatment group difference is no longer identified (tipping point analysis) (O'Kelly and Ratitch, 2014). These sensitivity analyses will only be conducted if the primary analysis identifies a statistically significant treatment group difference at 24 weeks in the MITT population.

Intercurrent concomitant therapy

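### The missing-not-at-random analyses run only on mITT, so treated patients with no post-baseline ESS are left out of the checks meant to test informative loss

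*SAP*

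**What the plan says.** SAP 9.1 fixes the population: "All efficacy analyses will be performed on the mITT population, the primary population". SAP section 5 (and Protocol 10.3) admits a randomised patient to mITT only if they took at least one dose "AND have at least one post-baseline efficacy measurement". The SAP describes patients who withdraw consent after receiving drug but "before the first follow-up visit and they may refuse to provide any follow-up assessments", and gives this reason for removing them: "Because these patients have no efficacy data to contribute to the analysis, they are excluded from the efficacy analysis populations". The only other efficacy set, per-protocol, is narrower.

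For missing data, SAP 9.3.1 will "use multiple imputation of missing data to generate multiple imputed complete datasets", complete through week 24. It then fits an ANCOVA of week-24 change on baseline, site and treatment and combines the results by Rubin's rules. One version imputes from placebo data; the other is a tipping-point analysis. Neither names a set wider than mITT, and both are run only if the mITT primary comparison is significant.

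Protocol 10.5 says that some participants are likely to leave without any post-baseline data. The note to Table 8 says that the MMRM power calculation "assumes 10% have no post-baseline data".

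**The concern.** Excluding a patient with no post-baseline score costs the MMRM essentially nothing, because the model would learn nothing about week-24 change from that patient. The imputation analyses are different. Under control-based imputation, baseline ESS, site and arm are enough to give the patient a week-24 value, so the stated reason for exclusion does not carry over.

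These analyses exist to ask whether a positive result depends on the missing-at-random assumption. As written, they ask it only of patients who gave at least one measurement. A positive result could then be described as robust to missing data although the patients about whom least is known were outside the check.

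**Working it through.** **1. Who is outside both analyses.** Among treated patients, only those with no post-baseline efficacy measurement. ESS is scheduled at every follow-up visit, so in practice this means no post-baseline ESS. Randomised patients who never took drug are also outside mITT.

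**2. The plan's own power.** Inputs (Protocol 10.5, SAP 6): 106:53 randomised, 96:48 analysed, difference 1.0, SD 1.7, two-sided alpha 0.044, correlation of baseline with change -0.4, correlation between visits 0.5.
- t-test: SE = 1.7 × √(1/96 + 1/48) = 0.301. Noncentral t power is 90.1%; the plan states 90%.
- MMRM: baseline-adjusted SD = 1.7 × √(1 - 0.4²) = 1.558, so SE = 1.558 × √(1/96 + 1/48) = 0.275. A dropout-weighted information calculation gives 94.6%; the plan states 94%.

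The stated power is reproduced. In the 10% discontinuation row, the Table 8 note implies that all discontinuations are patients with no post-baseline data: 10% of 159 is 15.9 (10.6 pomalidomide, 5.3 placebo).

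**3. Including these patients under control-based imputation.** Let f be the fraction of the pomalidomide arm imputed wholly from placebo, μ the placebo mean change and Δ the true difference. The pomalidomide mean becomes (1 - f)(μ + Δ) + fμ, so the difference becomes (1 - f)Δ. Imputing placebo patients from placebo leaves their mean unchanged.
- f = 0.05 (assumed): 0.95 × 1.0 = 0.95.
- f = 0.10 (the plan's overall allowance, applied to this arm): 0.90 × 1.0 = 0.90.

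**4. Simulation.** There were 1,500 trials per row, with 159 patients, 20 placebo-based imputations, ANCOVA, Rubin's rules, and alpha 0.0425 (the updated final level in SAP 7.7). Baseline mean 5.4 and SD 1.38, and a placebo change of -1.5, come from the large randomised nasal-spray trial in Protocol Table 6. Everyone else is complete at week 24, and site is omitted. Differences are in favour of pomalidomide.

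| True difference | No post-baseline ESS, each arm | mITT: estimate, power | Wider set: estimate, power | Trials losing significance |
|---|---|---|---|---|
| 1.0 | 5% | 0.99, 95.1% | 0.94, 93.6% | 1.5% |
| 1.0 | 10% | 1.01, 94.6% | 0.90, 91.4% | 3.2% |
| 0.7 | 5% | 0.70, 70.3% | 0.66, 66.7% | 3.7% |
| 0.7 | 10% | 0.71, 69.9% | 0.64, 60.9% | 8.9% |

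The value 0.7 is the minimally important difference cited in Protocol 10.5.

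**5. A borderline result.** Take an mITT result exactly at p = 0.0425 (z = 2.029) and hold the SE fixed.
- f = 0.05: z = 0.95 × 2.029 = 1.927, p = 0.054.
- f = 0.10: z = 0.90 × 2.029 = 1.826, p = 0.068.
- To stay significant at f = 0.10, mITT needs z = 2.029/0.90 = 2.254, or p of about 0.024.

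These fixed-SE figures somewhat overstate the shift. At f = 0.10 and Δ = 1.0, fixed-SE power is 89.2%, against 91.4% simulated.

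**The case against.** The strongest reply is that few treated patients should have no score at all. Under Protocol 7.3.5, a patient who permanently stops drug in cycle 1 is to complete the C1 visit and an end-of-study visit four weeks later, both with ESS. Under 7.3.6, withdrawal of consent calls for an early termination visit, which also includes ESS. SAP 3.2.4 recodes early termination visits made before the version 2.8 amendment, and within 28 days of the previous visit and dispensing, to the next cycle visit. SAP 9.3 includes all data whatever treatment was taken. This stands. A reader might infer that everyone who leaves before week 4 is dropped; the documents do not say that.

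A reader might also infer that the excluded patients are mainly rash losses, because Protocol Table 6 records "22% (2/9) due to rash at 2W" in the pomalidomide pilot. That is two patients, and nothing shows that they would have missed every visit under this trial's follow-up rules. Protocol 6.1.8.7 also reports 1 of 70 myeloma patients stopping for rash. No document links mITT exclusion to rash.

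Three further replies stand. The 10% is a planning assumption for the whole trial. mITT was prespecified in the protocol and is acceptable for the primary analysis. Treated patients without efficacy data still appear in the safety population, and reasons for withdrawal are to be listed.

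None of this explains why the imputation analyses stop at mITT. Follow-up rules reduce the number lost, but SAP 5 and Protocol 10.5 still expect some.

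**Conclusion.** The gap is real and modest. Treated patients with no post-baseline ESS are outside both missing-not-at-random analyses, and the reason given for excluding them does not apply to that method. The size rests on f, which the documents do not report for this trial, and on every such patient having taken drug. If f is close to zero, the wider analysis will change almost nothing.

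Two stronger readings should be avoided. First, it would be wrong to say that the planned control-based analysis shows no attenuation: it already pulls later dropouts within mITT towards placebo, and the loss computed here is additional. Second, the final site counts in SAP 7.6 sum to 145 (24 + 51 + 21 + 16 + 12 + 21) against 159 planned, and a reader might infer 14 exclusions. That section bases pooling on randomised patients, so the difference may simply be patients never enrolled.

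The primary analysis and the stated power are unaffected.

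**What to change.** Keep the mITT MMRM as primary and the two mITT sensitivity analyses as planned. In SAP 9.3.1, add both the control-based and the tipping-point analysis on all treated patients with a baseline ESS, that is, the mITT dose condition without the second condition. For those with no post-baseline value, impute week-24 ESS from baseline ESS and site: from placebo data in the control-based version, and over the planned range of departures for pomalidomide patients in the tipping-point version. State this set as an exception to SAP 9.1.

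An all-randomised version is optional. It adds patients who never took drug, whose loss cannot reflect toxicity.

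Report by arm the number treated with no post-baseline ESS, with reasons, so that f is visible.

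The cost is a few lines of SAP text and a little programming on data already collected. The drawback is a slightly less favourable sensitivity estimate.
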